******Protection against unknown risks******

To protect against this risk, we will do the following:

-During the informed consent process, participants will be notified about the possibility of unknown risks associated with taking lacosamide or their combination with alcohol.

-During the informed consent process, the possibility of unknown risks are explained and that researchers will let participants know if new information about risks and side effects becomes available over the course of the study.

-Adverse effects will be carefully monitored during each ADP lab session.

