3.3 Potential Risks and Benefits

3.3.1 Potential Benefits

There is no direct benefit to these participants besides referral to treatment, which will be provided at the end of the study. They will be able to withdraw from the study at any time. The direct benefit is not great for participants, but given the potential benefit to developing effective treatments for alcoholism, the risk-benefit ratio appears favorable.

Participants may benefit somewhat from the extra physical examination, laboratory tests, and attention. In the informed consent form, participants are instructed: "Taking part in this study may not make your health better. If you are in this study, you may benefit from the physical examinations, blood tests, and review of your symptoms. Others may benefit from the overall conclusions drawn from the results of this study."

AUD is major public health problem that contributes prominently to the global burden of disease [58]. While there are several approved medications for the treatment of AUD, the available pharmacotherapies are hampered by small effect sizes, adverse effects, and limited adoption into practice. Currently available FDA-approved pharmacological agents have major limitations and there is a critical need to identify novel medication strategies for AUD treatment. Despite the large numbers of patients who suffer from AUD, medications are greatly underutilized and only a small minority of adults in the

United States who have AUD are treated with medications. *This low utilization is thought to be in part due to a perception of AUD medication ineffectiveness.* The potential knowledge to be gained in this study is judged to be highly significant. This research seeks to expand the knowledge base regarding the treatment of alcohol use disorder. Because of the known low to moderate risk profile of the study medications and the close monitoring afforded by the study design, the level of risk for prospective participants is judged to be modest, and therefore, is considered to be reasonable, in comparison with the potential knowledge to be gained.

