4.2 Primary Objective

As this is a small pilot study, the Primary Aims are *process*- rather than *outcome*-oriented:

1. To establish the feasibility and safety of giving alcohol to human participants in a laboratory alcohol self-administration procedure;
2. To establish the feasibility and safety of administering AABM training sessions; and
2. To allow our research team to gain experience with these procedures and fine-tune them.

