6.1.3 Method of Assignment/Randomization

All participants will receive the active AABM training intervention.

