6.2.2.1 Adverse Events Definition and Reporting

Adverse Events

During the study, site personnel will note any change in the condition(s) and the occurrence and nature of any adverse events. Important clinical information that comes to light during study participation will be communicated by research coordinators to the study physician in real time.

The study physician (either the PI, [name]) will review each participant's safety at each study visit.

- Lab results will be reviewed on the same day that the results are received.
- Adverse effects reported by participants will be reviewed on the same day as they are reported by the study participant.
- Adverse effect assessment will be done by the research coordinators and discussed with the study physician on a daily basis, immediately after these adverse effects are reported by the participant to the study coordinator.

As with our current, CHR-approved clinical trials, the study physician, if not immediately present at the time of adverse effect data collection, will be contacted in real time by the study coordinator by phone, pager, or text message, so that adverse effects can be discussed with the study physician. The study physician, based on examination of the participant and/or review of the participant's data, will make a clinical judgment at each visit regarding whether it is safe to proceed with study medications.

The PI will report to the IRB, DSMB and study sponsor his assessment of the potential relatedness of each AE to protocol procedure, studied disease state, study drug via the CRF. For each adverse event recorded on the Adverse Event CRF, the PI will make an assessment of seriousness, severity, and causality.

According to the ICH guideline for Good Clinical Practice, an adverse event is any untoward medical occurrence in a clinical investigation participant administered a pharmaceutical product, regardless of causal attribution. An adverse event can therefore be any of the following:

- Any unfavorable and unintended sign (including an abnormal laboratory finding), symptom, or disease temporally associated with the use of a medicinal product, whether or not considered related to the medicinal product.
- Any new disease or exacerbation of an existing disease (a worsening in the character, frequency, or severity of a known condition).
- Recurrence of an intermittent medical condition (e.g., headache) not present at baseline.

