- Time-line Follow-back (TLFB): To collect alcohol and drug use in the 90 days prior to entry and all days included in the 11 weeks of the study. TLFB will be used to calculate standard alcohol containing drinks consumed per week in the past 90 days prior to consent and then throughout the 11 weeks of the study. Cigarette and substance use will also be collected by the TLFB.
- Biphasic Alcohol Effects Scale (BAES) [81]: Human Lab Sessions 1 and 2 (Table 1). This 14-item self-report rating scale measures alcohol stimulant/ sedative effects and is used regularly in the Yale ADP.
- Alcohol Urge Questionnaire (AUQ): At study entry; multiple times in Human Lab Sessions 1 and 2 (Table 1); 1-wk FU; 1-mo FU: The AUQ is an 8-item questionnaire assessing *desire, expectation of positive effect, and inability to avoid drinking if alcohol is available*. The AUQ is a reliable and valid scale for the measurement of self-reported alcohol urges. Its brevity and time frame for ratings (i.e. right now) makes it suitable for the ADP.
- Yale Craving Scale (YCS): multiple times during ADP Sessions 1 and 2. A measure of craving for alcohol.
- Ratings of Drinking Behavior During the Alcohol Self-Administration Period: multiple times in Human Lab Sessions 1 and 2. Subjects will be videotaped during the alcohol self-administration portion of ADP 1 and ADP 2. Videotapes will be rated by two independent for the onset and offset of each sip of alcohol. Dependent measures will be constructed including time until the first sip and average time to consume each drink.
- Vital Signs: Human Lab Sessions 1 and 2 (Table 1). These will include heart rate, blood pressure, and skin. The blood pressure cuff will be on subject's dominant arm while the probe of will be attached to the middle finger of the subject's non-dominant arm. These data will be further used to examine the safety of using the study medications during alcohol self-administration.

Neurocognitive Assessments:

The battery was developed to assess performance in cognitive domains commonly affected by heavy alcohol use and contains standardized instruments with good-to-excellent norms administered (~1.5 hours) at AABM sessions 1 and 9. Raw scores will be converted to z-scores. Domain-specific summary scores will be calculated by averaging z-scores of the individual constituent measures. When feasible, alternate forms will be used for repeated administrations.

Domains and constituent measures:

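### Four safety statements (a consent warning, the risk-level justification, the per-visit decision to proceed and the use of vital signs) refer to medications this trial does not give

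*Combined protocol and SAP*

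**What the plan says.** The interventions are set out in Section 6. Item 4 describes alcohol in two ADP sessions, and item 6 describes six sessions of AABM training. Section 6.1 treats the investigational treatment as computerized training, and 6.1.3 states: "All participants will receive the active AABM training intervention". The first two primary aims in 4.2 are "To establish the feasibility and safety of giving alcohol to human participants in a laboratory alcohol self-administration procedure" and "To establish the feasibility and safety of administering AABM training sessions".

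Four statements elsewhere concern medication:

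- **Consent (3.3.2, protection against unknown risks, first bullet):** "participants will be notified about the possibility of unknown risks associated with taking lacosamide or their combination with alcohol".
- **Risk level (3.3.1, closing sentence):** the rating of modest risk is introduced by "Because of the known low to moderate risk profile of the study medications and the close monitoring afforded by the study design".
- **Visit decision (6.2.2.1):** the study physician "will make a clinical judgment at each visit regarding whether it is safe to proceed with study medications".
- **Vital signs (6.3.5, measures of alcohol effects):** the data are also to be used to "examine the safety of using the study medications during alcohol self-administration".

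**The concern.** These are not background sentences. The first tells staff what to say during consent, and the third tells the physician what to decide at each visit. The second supports the overall risk rating, and the fourth says what a set of safety data is for.

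Followed literally, staff would warn participants about a drug they will not take. The stated decision to proceed would concern something absent, and would not say whether the next alcohol or training session may go ahead. The risk rating would rest partly on a product outside the study. Because safety is part of the primary aims, its supporting text should refer to the procedures whose safety is being studied.

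**Working it through.** No arithmetic applies. The protocol has no sample-size calculation (6.4.2) and plans no inferential statistics (6.4.1). The check compares texts.

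**Step 1. Is any drug given?** Section 6 items 1 to 7, Section 6.1, the schedule in 6.3.1 and the visit table in 6.3.5 list alcohol sessions, training sessions, phone calls, assessments and follow-up. None lists a study medication. Some sections mention random assignment or a sham condition (3.2; Section 6 item 6; the 6.3.5 table), whereas 6.1.3 gives active training to all. That conflict does not affect this point, because neither reading includes a drug.

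**Step 2. What does each statement refer to, and what else in the protocol serves the same function?**

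| Function | Refers to | Text elsewhere that needs no drug |
|---|---|---|
| Consent warning (3.3.2) | Lacosamide, alone or with alcohol | Second bullet of the same list explains unknown risks in general; the alcohol-challenge safeguards say the consent form will address leaving a session early |
| Risk level (3.3.1) | Study medications, plus close monitoring | An earlier sentence in 3.3.1 finds the risk-benefit balance favorable without naming a drug; 3.3.2 sets out alcohol risks and safeguards |
| Visit decision (6.2.2.1) | Study medications | The same section has the physician review each participant's safety at every visit; withdrawal rules in 3.3.2 and 6.3.6 |
| Vital signs (6.3.5) | Study medications during self-administration | The general listing in 6.3.5 schedules vital signs at entry and during each laboratory session, with no medication purpose |

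Lacosamide is named only in the consent bullet. The other three statements say study medications without naming one.

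**Step 3. What remains uncovered?** The general text does not correct the specific text. In 6.2.2.1 the general safety review is followed by a specific decision on medications, so staff have to infer that the alcohol and training sessions are meant. In 3.3.1 two reasons are given for the modest rating: the medications' profile and close monitoring. Only the second applies here. Section 3.3.2 describes no risk specific to AABM, although AABM safety is a primary aim.

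**Step 4. Is it isolated?** No. In 6.2.2.1, SAE collection starts once the participant has consented and received study drug, and runs for 7 days after the last dose. Nobody receives a dose, so read literally the window never opens. Every SAE would then fall under the pre-drug exception, which collects only events the investigator thinks a protocol procedure may have caused. The same section requires SAEs to be reported to the sponsor within 24 hours whatever their relationship, so it also conflicts with itself. Section 6.4.3.2 plans to describe alcohol-medication interaction effects, which cannot be estimated here.

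**Step 5. Reach.** Section 5.3.1 enrolls 12 and expects to start up to 15. Consent precedes screening (6.3.3), so the consent instruction also reaches people who fail screening; their number is not stated.

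**The case against.** The strongest reply is that this is leftover template wording and that the protocol manages the real hazards in text that does not depend on a drug.

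- **Before the first alcohol session:** 5.3.2 excludes medical conditions that contraindicate alcohol, and 6.3.4 enrolls only when participation is judged safe.
- **At the sessions:** withdrawal assessment, breath alcohol, urine drug screen and a medication review are scheduled before each laboratory session. Adverse effects are monitored during it and asked about at training visits.
- **Between and after sessions:** 3.3.2 provides for withdrawal on a sustained increase in drinking between the two ADP sessions, on unacceptable events related to study interventions, or on any outcome that makes continuing unsafe. Section 6.3.6 adds discontinuation rules, and 7.5 halts the study for a study-related serious event.

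All of this stands. A reader might infer from the four statements that nothing in the consent, risk or visit-safety text covers alcohol or AABM, or that no rule governs whether an alcohol session goes ahead. The documents do not support either inference.

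A reader might also infer that the consent form itself misinforms participants. That cannot be judged, because the consent pages are not in the review copy. The consent wording that the protocol does quote, in 3.3.1 and in the privacy part of 3.3.2, mentions no drug.

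The reply does not make the four statements correct. A wrong specific instruction beside a sound general one leaves staff to decide which to follow.

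**Conclusion.** The point holds as an internal contradiction in operative safety text. Four statements refer to medications that the trial does not give, and they conflict with Section 6 and 6.1.3. It should be corrected, but it does not show that any participant or visit is unprotected.

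Its reach is wide: one consent instruction for everyone who consents, one decision at every visit, one of two reasons for the risk rating, and one stated use of vital signs. Its practical depth is limited, because the safeguards that need no drug cover much of the same ground. Of the related wording, the SAE window has the most direct effect on data, since it decides which serious events are collected.

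The conclusion assumes that the absence of a drug from the Methods, schedule and visit table is intended. Section 6.1.3 and the heading of 6.1 support this. It assumes nothing about the content of the consent form.

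**What to change.** Reconcile the four statements with the interventions in Section 6 and 6.1:

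- **3.3.2:** delete lacosamide from the consent instruction, and check the consent form for the same carry-over.
- **3.3.1:** restate the reason for the risk level in terms of the alcohol and AABM procedures. Because 3.3.2 is silent on AABM, it should say what risk, if any, is expected from the training.
- **6.2.2.1:** reword the per-visit decision to refer to the study procedures. The content of any clinical rule is for the study physician.
- **6.3.5:** restate the purpose of the vital-signs data in the same terms.

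In the same amendment, define the SAE collection window in 6.2.2.1 by events that occur in this trial and reconcile it with the 24-hour reporting rule. Remove the medication-interaction item from 6.4.3.2 or restate it for what is measured. A search for study drug and study medication would find the rest, including the references in 6.3.6.

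The cost is a wording amendment and a consent-form check. Sample size, visits and the descriptive analysis approach do not change.

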4. STUDY OBJECTIVES

4.1 Hypothesis

Include a clearly defined hypothesis, if relevant, and list the key questions the study is expected to answer. Be detailed, clear and as specific as possible.

4.2 Primary Objective

As this is a small pilot study, the Primary Aims are *process*- rather than *outcome*-oriented:

1. To establish the feasibility and safety of giving alcohol to human participants in a laboratory alcohol self-administration procedure;
2. To establish the feasibility and safety of administering AABM training sessions; and
2. To allow our research team to gain experience with these procedures and fine-tune them.

4.3 Secondary Objectives

The Secondary Aim is to obtain a preliminary assessment of the effects of Alcohol Approach Bias Modification training on alcohol consumption and related behaviors in individuals with AUD.

5. STUDY DESIGN

5.1 General Design

We will conduct the first pilot trial of AABM effects on alcohol consumption in the human laboratory in individuals with AUD and the first trial of AABM effects on the Yale Alcohol Drinking Paradigm - a method of rapidly assessing the potential efficacy of putative pharmacologic and possibly behavioral treatments for AUD. Participants will be 12 non-treatment-seeking heavy-drinking male volunteers. After baseline assessment, participants will undergo Human Lab session 1, in which we will administer the Alcohol Approach-Avoidance Task (AAT) (not AABM training) to measure baseline (pre-treatment) alcohol approach bias tendency, and then conduct the ADP to measure baseline alcohol consumption. After Human Lab/ADP Session 1, participants get 2 weeks of a total of 6 sessions of training. Outcomes will

be various measures of feasibility, including recruitment, retention, safety, and adverse effects and assessment of measurement burden, and the tolerability of ADP and AABM interventions.

5.1.1 Study Duration

The study begins with a screening visit that is expected to last approximately 4 hours. If it is deemed safe for the participant to enroll in the study and they meet all eligibility criteria, then the participant will be scheduled for 2 human lab sessions, each 12 hours long. The human lab sessions will take place on Week 2 (1st human lab session) and Week 5 (2nd human lab session). After each human lab session, a study coordinator will conduct a phone visit which is estimated to take 10 minutes. In addition to the human lab sessions, participants will come to the Ft. Miley campus 3 times per week for 3 weeks to complete Alcohol Approach Bias Modification (AABM) training sessions. These computerized training sessions last 20-30 minutes and will occur during Weeks 3 and 4 of the study. A follow-up visit will be scheduled 7 days after the 2nd and final human lab session. In total, participants can expect to spend about 32 hours over the course of 6 weeks.

5.2 Outcome Variables

This section describes the primary and secondary outcome variables, which are the endpoints that will be used to assess the study.

5.2.1 Primary Outcome Variables

The primary outcome variables are measures of feasibility:

1. Time needed to recruit, screen, and run the study procedures for 12 participants.
2. Retention rates at the various in the study process (screening, Human Lab ADP session 1 + 2, AABM training sessions 1 – 6, and follow-up).

5.2.2 Secondary Outcome Variables

Secondary outcomes:

1. Alcohol craving
2. Alcohol consumption during each of the 2 Human Lab ADP sessions.

5.3 Study Population

A total of 12 male non-treatment seeking healthy community volunteers will be enrolled.

5.3.1 Number of Participants

The study will enroll 12 men participants. We anticipate needing to start up to 15 participants to get 12 to complete 2 human lab sessions and the majority of the 6 AABM training sessions.

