6.3.4 Enrollment

Once a participant has completed all screening/baseline measures and procedures and it has been determined that the participant is eligible and it is safe to participate, then they will be enrolled in the study.

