6.4.3.1 Primary Analyses

Primary analyses will consist of descriptive statistics. These measures of feasibility are:

1. Time needed to recruit, screen, and run the study procedures for 4 participants
2. Retention rates at the various timepoints in the study process (screening, Human Lab ADP session 1,2,3, and follow-up).

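### Sections 5.3 and 5.3.1 give 12 as the number enrolled, but 5.3.1 read with 6.3.4 implies up to 15 enrolled and 12 completers, so the same completion data can be reported as 80% or 100%

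*Combined protocol and SAP*

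**What the plan says.** Two places in the protocol give 12 as the number enrolled. Section 5.3 says "A total of 12 male non-treatment seeking healthy community volunteers will be enrolled", and 5.3.1 opens with "The study will enroll 12 men participants". The next sentence of 5.3.1 reads "We anticipate needing to start up to 15 participants to get 12 to complete 2 human lab sessions", and adds "the majority of the 6 AABM training sessions" to what a completer must do.

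Section 6.3.4 fixes the moment of enrollment. When the screening and baseline procedures are done and the man is judged eligible and safe to take part, "then they will be enrolled in the study". Step 3 of section 6 has eligible men move on from there to the two lab sessions and six training sessions.

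The two primary outcomes in 5.2.1 are "Time needed to recruit, screen, and run the study procedures for 12 participants" and "Retention rates at the various in the study process (screening, Human Lab ADP session 1 + 2, AABM training sessions 1 – 6, and follow-up"). Section 6.2.1 repeats both. Section 6.4.3.1 carries them into the primary analysis in different terms: time is for 4 participants, and retention is "Retention rates at the various timepoints in the study process (screening, Human Lab ADP session 1,2,3, and follow-up"), with the training sessions left out. None of these sections states the denominator of a retention rate, and the protocol does not define what it means to start.

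**The concern.** The figure 12 counts enrolled men in one sentence and completers in the next. On the definition in 6.3.4, a man who begins the lab and training sessions is already enrolled. If 15 begin and three are lost, 15 were enrolled and the stated study size of 12 is wrong.

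This would be minor if retention were incidental, but it is one of only two primary outcomes. The analysis is purely descriptive (6.4, 6.4.1), so the reported percentage is itself the result. Section 2.1 says the pilot data and feasibility demonstration are meant to support later funding proposals. A base left open until the data are in can be chosen after the attrition is known.

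**Working it through.** **Inputs**
- Enrolled: 12 (5.3 and the first sentence of 5.3.1).
- Started: up to 15; completers sought: 12 (second sentence of 5.3.1).
- Enrollment point: after screening and confirmation of eligibility (6.3.4), before the lab sessions (section 6, step 3).
- Dropout rate: not stated.

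**Step 1: check the plan's own pair of numbers.** The loss implied by 15 and 12 is (15 − 12)/15 = 3/15 = 20%. Inflating 12 for a 20% loss gives 12/(1 − 0.20) = 15, which matches. This shows consistency only, because the 20% was derived from the same two numbers.

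**Step 2: test whether 12 enrolled and 12 completers are compatible.** If 12 men were enrolled and the implied 20% loss fell on them, 12 × 0.80 = 9.6 would be expected to complete. Twelve enrolled give 12 completers only if nobody is lost after enrollment.

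**Step 3: compute completion under each base.** Completion rate = completers / base, with 12 completers.

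| Men started | 12 / started | 12 / 12 |
|---|---|---|
| 13 | 92.3% | 100% |
| 14 | 85.7% | 100% |
| 15 | 80.0% | 100% |

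The largest gap is 100% − 80% = 20 percentage points, at 15 starters. These figures describe completion as 5.3.1 frames it (both lab sessions and most of the training), not retention at each stage.

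**Step 4: place the losses.**
- *All three lost after eligibility is confirmed.* Under 6.3.4, 15 were enrolled, which contradicts 5.3, and completion among enrolled men is 80%.
- *All three lost before enrollment.* Then 12 were enrolled, 5.3 is right, and completion is 12/12 of enrolled and 12/15 of started.

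In both cases the rate depends on a base that the plan does not state. Because retention is listed from screening onward, the number consented or screened is a third possible base; its expected size is not given.

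**Step 5: set the primary-analysis section beside the outcome section.** Section 5.2.1 has 12 participants, ADP sessions 1 and 2, and training sessions 1 to 6. Section 6.4.3.1 has 4 participants, ADP sessions 1, 2 and 3, and no training sessions. Fixing the denominators alone would leave this conflict in place.

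**The case against.** The best defence is that starting may mean attending screening. Section 5.1.1 describes the study as beginning with a screening visit, and 6.3.4 puts enrollment after it, so 15 could start and 12 be enrolled without contradiction. That reading is possible. It requires that nobody be lost after enrollment, and it sits awkwardly in a sentence about completing lab and training sessions. It also leaves the denominator open.

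Other points on that side stand. The 12 and the 15 are adjacent sentences of 5.3.1, so nothing is concealed. The wording is up to 15, which makes 80% the low end of the planned range. A completers-only base is not the natural choice for rates listed from screening: it would make screening retention meaningless and both lab-session rates 100% by construction. In a descriptive study this small, counts can easily be shown as n/N.

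A reader might infer three stronger things that the documents do not support:
- *That drop-outs are replaced until 12 complete, so near-complete retention could be reported whatever the attrition.* Section 5.3.1 gives a forecast. No section states a replacement rule.
- *That the time outcome has a known chance of never being observed.* If true completion were 80%, 15 starters would give at least 12 completers with binomial probability 0.648, leaving about 35% short. That figure needs a firm stop at 15 and a reading of 12 participants as 12 completers, and the plan states neither. The 80% is also only implied by 12 of 15.
- *That accepting most of the six training sessions conflicts with the recommended session numbers in section 2.2.1.* That is a separate matter, and 5.2.1 already lists retention across training sessions 1 to 6.

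**Conclusion.** The point holds in a limited form and should be corrected. Unless all losses come before enrollment, the stated size of 12 conflicts with the plan's own definition of enrollment: up to 15 men are enrolled and 12 is the completer target. Completion can then be reported as 80% or 100% with 15 starters, 86% or 100% with 14, and 92% or 100% with 13.

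The size rests on two assumptions: that exactly 12 men complete, and that starting means entering the lab and training sessions. If starting means screening, the conflict over the number enrolled disappears, but the missing denominator remains. What is shown is an unreconciled sample size and an unstated base for a primary outcome. It is not shown that the trial would hide attrition or fail to reach its target.

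**What to change.** - **Sections 5.3 and 5.3.1:** state that up to 15 men will be enrolled, as defined in 6.3.4, to obtain 12 completers.
- **Sections 5.2.1, 6.2.1 and 6.4.3.1, retention:** use consented men as the base at screening. Use all enrolled men, including those who drop out, as the base for ADP 1, training sessions 1 to 6, ADP 2 and follow-up.
- **Same sections, time outcome:** say whether the 12 participants are enrolled men or completers. If that number is not reached, report the elapsed time and the number reached.
- **Section 6.4.3.1:** reconcile the 4 participants and the three ADP sessions with the 12 participants, two ADP sessions and six training sessions in 5.2.1 and 6.2.1.

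The cost is an edit to the text; no visit or measurement is added. The downside is that reported retention may be less favourable than on a base of 12.
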